3.2.1 Referrals to a primary care provider (PCP)

- If food pantry client is not (and will not be) enrolled in FAITH-DM, provide resource hand out
 - For clients who report no PCP, complete “Screening and Referral Form” and fax form to appropriate provider
- If participant is enrolled in FAITH-DM, study staff will ask: “Is there a doctor, other health care provider, or clinic you usually go to in order to help you manage your diabetes?”
- Intervention participants who answer “yes” (has PCP)
 - Retrieve PCP information
- Intervention participants who answer “no” (does not have PCP)
 - Provide written information to participant on PCP resources

- Send active referral to PCP (FAX to PCP and/or phone call to PCP/clinic) using the appropriate HCUA provider letter (see **section 7.7**).
- Control participants who answer “yes” (has PCP)
 - Retrieve PCP information
- Control participants who answer “no” (does not have PCP)
 - Provide resource handout
- All study participants will again be asked at T6 and at T12 if they have a PCP; for **both** intervention group and control group participants who report no PCP at T6 or T12, provide:
 - Written information to participant on local PCP resources
 - Active referral to PCP (FAX to PCP and/or phone call to PCP/clinic) using the appropriate HCUA provider letter (see **section 7.7**).

See **Appendix AI** for the “Screening and Referral Form” to use when sending a food pantry client’s screening results to a clinic. The client must sign this form, giving food bank staff permission to share screening results with the clinic and/or provider.

Food banks must also maintain a HIPAA compliant fax to send/receive client information to/from health care partners in order to maintain security and protect client/patient medical information. To meet HIPAA standards, food banks should ensure that a dedicated FAITH-DM fax is located in a secure area (away from public areas). Staff should use the HIPAA-compliant fax cover sheet (**Appendix AB**) whenever faxing forms and information connected with the FAITH-DM study. Additionally, site staff should follow best practices to maintain protection of participant data:

- Only authorized personnel are to have access to the fax machine and incoming faxes
- Destination numbers should be verified before transmission
- Verified numbers used frequently should be pre-programmed to reduce number entry errors
- Recipients should be notified that they have been sent a fax

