3.6 Length and time windows for intervention

For participants in the intervention group, access to the food package and DSME intervention components is only available during their 6-month intervention window (T0-T6). Intervention group participants should no longer have access to these elements after they reach their T6 time point in the study (they will have access to referrals for care, if needed, at T6 and T12, and have access to HbA1c testing and monitoring at T6 and again at T12).

For participants in the control group, access to the food package and the modified DSME intervention components is also only available during their 6-month intervention window (T6-T12). Control group participants should not have access to intervention components prior to T6, nor should they continue receiving any intervention components after T12. Control group participants will have access to referrals for care, if needed, at T6 and T12, and have access to HbA1c testing and monitoring at T6, T9, and again at T12 per existing study protocols.

Site adherence to these time windows will help achieve and maintain fidelity to the original study design. While sites may need to make minor, reasonable accommodations for individual participants (e.g., provision of a maximum of 2 food packages to be picked up within 1 month post T6 follow-up activities for intervention group participants), any deviation from these protocols should be logged in the MS Access database for the participant, and site staff should complete and submit a Protocol Deviation (**Appendix F**) form.

Any food bank services (e.g., food packages, education, support, referrals) provided or conducted after T12 activities for any study participant will be at the discretion of the food bank as these clients will no longer be enrolled in the study as active study participants.

4 Recruitment and Retention Plan

In order to meet recruitment targets, we will:

- Monitor recruitment and intervene quickly to change recruitment techniques that are proving unsuccessful; discuss on monthly calls
- Identify barriers to recruitment
- Use multiple recruitment strategies depending on the needs of each food bank or food pantry (see **Appendix AJ** for a sample recruitment flyer to post at pantry sites)
- If we are not meeting recruitment goals, we can employ additional outreach strategies such as English and Spanish language flyers and advertisements

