7.7.8 Provider Packet Summary Table

The table below summarizes the different types of provider packets to be assembled at baseline and follow-up based upon the participant’s enrollment in the intervention or control group and their reporting of a PCP:

	Intervention group	Control group
Existing PCP	
At T0: HCU Letter 1 - T0 Current Pt INT, signed forms, information sheets
 
At T6: HCUS, HCU Letter 4 - T6 Current Pt, signed forms
 
At T12: HCUS, HCU Letter 7 – T12 Current Pt, signed forms
	
At T0: HCU Letter 3 - T0 Current Pt CONT, signed forms, information sheets
 
At T6: HCUS, HCU Letter 4 - T6 Current Pt, signed forms
 
At T12: No provider communication

No existing PCP (at T0)	
At T0: HCU Letter 2 - T0 Newly Referred Pt INT, signed forms, information sheets
 
At T6: HCUS, HCU Letter 4 - T6 Current Pt, signed forms
 
At T6: If participant still doesn't have PCP: HCU Letter 5 - T6 Newly Referred Pt, HCUS, signed forms, information sheets
	
At T0: No provider communication, but participant will be encouraged to see PCP
 
At T6: If participant now has PCP: HCUS, HCU Letter 4 - T6 Current Pt, signed forms, information sheets
 
At T6: If participant still doesn't have PCP: HCU Letter 5 - T6 Newly Referred Pt, HCUS, signed forms, information sheets

	
At T12: HCUS, HCU Letter 7 – T12 Current Pt, signed forms
 
At T12: If participant still doesn't have PCP: HCU Letter 8 – T12 Newly Referred Pt, HCUS, signed forms, information sheets
	
At T12: If participant now has a PCP, no provider communication
 
At T12: If participant still doesn't have PCP, use "Screening and Referral Form" to complete active referral

--	---	--

8 Randomization

In randomized, controlled clinical trials, participants are assigned to a treatment group based upon a pre-determined randomization scheme developed by the study statistician ([name], UCSF). Randomization is used to reduce bias in assignment to treatment. In our case, clients will be randomized to receive the intervention immediately or after a 6-month delay.

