10.2 Blood glucose > 240 mg/dL, or HbA1c > 9% (Hyperglycemia)

- The GE100 Blood Glucose Monitor displays results between 20 and 600 mg/dL (if a test result is over 600 mg/dL, the meter will display “Hi” – in this event, repeat test to confirm glucose level; perform QC check on meter as necessary).
- The A1C+Now system displays test results up to 12.9% (for results greater than 12.9%, the device will display > 13%).
- If a participant (or client not yet enrolled in the study) has a blood glucose result between 240 – 399 mg/dL, or a HbA1c result between 9% - 12.9%, study staff should refer the client back to their primary care provider for evaluation. If the client or participant does not have a primary care provider, study staff should make a new patient referral to a partner clinic following study protocols. Partner clinic agreements contain recommended timeframes for contacting referred patients with these results (within 1 week) to schedule a patient appointment to occur within 1 month from receiving the referral.
 - Hyperglycemia in the absence of symptoms does not require action by study staff or reporting as an adverse event; all testing results should be recorded and saved in the MS Access database.
- If a participant (or client not yet enrolled in the study) has a blood sugar greater than 400 mg/dL (or confirmed “Hi” reading on the glucometer), or a HbA1c result > 13%, study staff should refer the client back to their primary care provider and/or facilitate an appointment being made. If the client or participant does not have a primary care provider, study staff should make a new patient referral to a partner clinic following study protocols.
 - Food bank – clinic partnership agreements outline that clinics will attempt to contact referred clients with these results within 24 hours, and will schedule appointments for clients experiencing severe hyperglycemia within 72 hours of receiving a referral from the food bank.
 - All clients with severely elevated blood glucose results should also be encouraged by study staff to initiate contact with their PCP or nearest community clinic.
 - Hyperglycemia in the absence of symptoms of study staff action does not require reporting as an adverse event; all testing results should be recorded and saved in the MS Access database.

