13.5.2 Health care utilization indicators and hypotheses

One of the four arms of the intervention is the active referral to a primary care provider if the participant does not have one at the time of enrollment. In addition, the self-management support (SMS) activities in the intervention are designed to reinforce engagement of the participant with the primary care provider as a component of their diabetes management. Thus, our primary indicator will be change in the reported utilization of primary care services, as assessed by self-reported data and provider reports where available.

Our hypothesis is that the intervention participants will have increased engagement with their primary care provider when compared to the control group, and when compared to their level of engagement prior to the intervention. Because this particular model is unique in its use of food pantries as a point of outreach and support and its incorporation of a diabetes-focused food security intervention, there is no prior literature that directly informs our hypothesis development. However, we can draw some insight for hypothesis development from other studies of the impact of self-management support models on health care utilization. For example, Hamid et al. (2014) reported on a cluster-randomized design used to assign 268 diabetes patients to a nurse-community health worker intervention or usual care. Hospitalizations, emergency department, and primary care physician visits were collected retrospectively for one year prior to, and during, the intervention to assess changes in health care utilization. Adjusted incidence rate ratios for primary care physician visits were significantly higher in the community health worker intervention relative to the usual care. The authors found no main intervention effect on emergency department utilization, but visits in the prior year modified the intervention effect on emergency department visits. Increased primary care physician utilization was associated with greater decreases in HbA1c.

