Patient Referrals

1. If the FOOD BANK accepts direct referrals from organizations:
 - a. Upon receiving a patient referral from The Organization, the FOOD BANK will be responsible for contacting the patient per existing food bank protocols to assess eligibility for participation in any food bank or partner agency food program.
 - b. The FOOD BANK will make at least three (3) attempts to contact the referred patient. If the FOOD BANK is unable to contact the patient, or if the patient declines to participate in any food distribution / pantry program, then the referral will be closed and the FOOD BANK will notify The Organization that the referral was closed.
2. FOOD BANK FAITH-DM staff will screen food bank clients for type 2 diabetes risk and control at existing food distribution sites using Point-of-Care blood glucose and HbA1c testing.
3. If the Organization accepts direct referrals, the FOOD BANK will refer clients to The Organization who are assessed as being at risk (HbA1c result $\geq 5.7\%$) and who state they are without a primary medical provider. By identifying and referring these clients, the FOOD BANK aims to facilitate a

process for clients to establish medical care and receive follow-up evaluation regarding diabetes risk and/or health status.

- a. For food bank clients with an HbA1c result $\geq 9.0\%$, The FOOD BANK will refer clients to The Organization if they state they are without a primary medical provider (and live within The Organization's service area), or if they state that they already receive care at The Organization.
 - b. The FOOD BANK will complete a "Screening and Referral Form" indicating the dates of screenings, HbA1c and other screening results, and additional client information for food pantry clients not enrolled in the FAITH-DM trial (see attached document: *FAITH-DM Screening and Referral Form*)
 - c. The FOOD BANK shall obtain client consent to share Protected Health Information (PHI) with The Organization.
 - d. The FOOD BANK will fax completed referral forms to The Organization.
4. If the Organization does NOT accept direct referrals from any agency, then the FOOD BANK will provide clients needing care with written information, verbal instructions, and encouragement for the client to make a new appointment with their existing PCP or a new patient appointment at the Organization by using the Organization's existing patient appointment scheduling process.

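### At T0, section 10.2 directs a partner-clinic referral for any participant with a high result and no PCP, the control-arm rules give only a handout, and no readable text says which prevails

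*Combined protocol and SAP*

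**What the plan says.** **The safety rule.** Section 10.2 has two tiers: glucose 240–399 mg/dL or HbA1c 9%–12.9%, and glucose above 400 mg/dL or HbA1c above 13%. Each applies to a participant or to a client not yet enrolled. In both tiers, "If the client or participant does not have a primary care provider, study staff should make a new patient referral to a partner clinic"; the sentence goes on to say that study protocols are to be followed, without naming a section. The lower tier adds that hyperglycemia without symptoms calls for no staff action. The matching line in the severe tier waives only adverse event reporting. The draft clinic agreement (Appendix O, food bank item 3a) points the same way for HbA1c of 9.0% or more: "The FOOD BANK will refer clients to The Organization if they state they are without a primary medical provider".

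**The arm rules at T0.** Section 3.2.1 gives an intervention participant without a PCP an active referral and a control without one a resource handout. Section 7.7.2.4 calls the latter a passive referral and requires no provider packet. The 7.7.8 table lists, for this group at T0, "No provider communication, but participant will be encouraged to see PCP". Section 13.5.1 repeats the split by arm, and the baseline enrollment form (Appendix AM) offers only active for intervention and passive for control. None of these mentions a high result.

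**Text on timing and on what counts as intervention.** Section 3.6: "Control group participants should not have access to intervention components prior to T6", and "Control group participants will have access to referrals for care, if needed, at T6 and T12". Section 13.5.2: "One of the four arms of the intervention is the active referral to a primary care provider".

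**The concern.** A control with a very high HbA1c and no doctor is handled differently depending on which page the staff member follows. Under 10.2 the person is referred to a partner clinic. Under the control-arm rules the person leaves with a handout and encouragement, and the next scheduled referral point is T6, at 5 to 7 months. Sites can therefore differ in a matter of participant safety.

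There is also an anomaly. For a screened client who does not enroll, section 3.2.1 tells staff to "provide resource hand out" and, if there is no PCP, to complete the referral form "and fax form to appropriate provider". On the arm rules alone, an enrolled control gets less.

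For the analysis, the T0 difference in referral between arms is left undefined. Active referral is part of the stated reason for the utilization analysis's primary indicator, change in primary care use (13.5.2).

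**Working it through.** The conflict is textual and needs no arithmetic. The numbers at the end only give its scale.

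**Can one reading satisfy every rule?**

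- *Who is covered.* 10.2 covers every participant; the arm rules cover every control without a PCP at T0. A control with no PCP and a 10.2 result is under both.
- *What is done.* 10.2 gives a new patient referral to a partner clinic. The arm rules give a handout. A handout is not such a referral, so doing only what the arm rules list leaves 10.2 unmet.
- *Does the pointer to study protocols settle it?* No. It names no section, and no T0 referral route is written for this group. HCU Letter 2 is for intervention participants (7.7.2.2). The Screening and Referral Form is for people not enrolled (3.2.1; Appendix O item 3b; Appendix AR). At T12, by contrast, the 7.7.8 table assigns that form to controls without a PCP.
- *When.* At T6 and T12, 3.2.1 gives active referral in both arms, so the conflict is confined to T0.

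**Scale.** Inputs: planning mean 9.5 and SD 1.6 (13.4.1); entry limit 7.5% (5.2); 720 recruited and allocated equally, so 720 / 2 = 360 controls. Three distributions starting at 7.5 were matched to mean 9.5 and SD 1.6, with d = 9.5 − 7.5 = 2.0:

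- 7.5 + gamma, shape d²/SD² = 4/2.56 = 1.5625, scale SD²/d = 1.28: P(≥9) = 0.527, P(≥13) = 0.0389.
- 7.5 + lognormal, σ² = ln(1 + 2.56/4) = 0.495, μ = ln 2 − σ²/2 = 0.446: P(≥9) = 0.523, P(≥13) = 0.0367.
- Truncated normal, underlying mean 6.26 and SD 3.01: P(≥9) = 0.532, P(≥13) = 0.0368.

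The share of controls without a PCP is not given. Section 13.5.3 says most pilot enrollees reported having one. As an assumption, take 5% to 30%. The upper end is the complement of that section's 70% goal for provider data in the control arm. Then 360 × 0.05 = 18 and 360 × 0.30 = 108.

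- Both tiers: 18 × 0.523 = 9.4 to 108 × 0.532 = 57.5, about 9 to 57.
- Severe tier: 18 × 0.0367 = 0.7 to 108 × 0.0389 = 4.2, roughly 1 to 4.

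These count HbA1c only and assume that it does not depend on PCP status. If the mean among controls without a PCP were 9.0 to 10.0 (SD 1.6), the share at 9% or more would be 0.33 to 0.72, so 18 × 0.33 = 6 to 108 × 0.72 = 78. If 9.5 and 1.6 described a normal population before the 7.5% limit, the shares would be 0.696 and 0.016. The severe-tier count would then be 18 × 0.016 = 0.3 to 108 × 0.016 = 1.7.

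**The case against.** The best case against is that the rules can be followed together. Section 7.7.2.4 says only that no packet is required, which does not forbid a referral, and 7.7.8 summarizes survey packets and is not a safety rule. A handout plus a 10.2 referral would honor both 3.2.1 and 10.2. HbA1c is tested before randomization and 10.2 names clients not yet enrolled, so its instruction can arise before any arm rule applies. All of this stands as the sensible reading, but nothing tells staff to adopt it, and the 7.7.8 wording and the two-box form steer them away from it.

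The lower-tier line about no action also has force. It sits directly under a referral instruction, says nothing about arm, and can be read as meaning emergency response. It does not say so, and therefore the clean conflict is in the severe tier.

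Several stronger readings are tempting and are not supported:

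- *That 10.2 makes referral mandatory.* It says staff should refer, so it directs.
- *That 3.6 forbids the referral.* Its control paragraph opens with food packages and modified education, and controls have their HbA1c tested at T0 although testing is itself one of the four components. The bar most naturally means food and education. Listing referrals at T6 and T12 does not exclude a safety referral at T0.
- *That such a referral is a protocol deviation.* Neither section 11 nor Appendix F lists it. Staff might think so, because 13.5.2 counts active referral as intervention.
- *That the clinic agreements bind the food banks.* Appendix O is a draft, is not written by arm, and applies item 3 where the clinic accepts direct referrals.
- *That clinic contact times conflict* (24 hours in 10.2, 24–48 hours in Appendix O). The signed agreements are not in the documents, so no conflict is shown.

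A control also receives written results with clinic information, so the person is not left uninformed.

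**Conclusion.** The concern holds for T0. For a control with no PCP and a 10.2 result, the plan gives two different instructions, and no readable text ranks them. The screening flow chart and the T0 utilization flowchart are not shown and the provider letters are not included, so this is established for the readable text only.

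The severe tier is the firm part. The lower tier is weaker, because 10.2 qualifies itself there. The head counts (roughly 1 to 4 severe, about 9 to 57 overall) rest on an assumed PCP share and on the planning mean and SD, and should be read as orders of magnitude.

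A reader might infer bias in the primary HbA1c result or a measurable dilution of the utilization contrast. The documents do not allow either to be sized, and neither is claimed. The case for change is participant safety and consistent practice across sites. It is a cheap improvement.

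**What to change.** 1. In 10.2, state that a result in either tier triggers the partner-clinic referral in both arms at T0 when there is no PCP, in addition to the handout, and that this is not a protocol deviation. Name the form to use.
2. Cross-refer to that sentence in 3.2.1, 7.7.2.4, 7.7.8 and the enrollment form, so that a control can be recorded as referred under 10.2.
3. Reword the lower-tier line so that it does not cancel the referral, for example by limiting it to emergency action.
4. Log these referrals in the Access primary care contact form (12.3.6) and report them by arm in the utilization analysis.

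The cost is one sentence, a few cross-references and a form edit. The contact form already exists, so no new data field is needed for the log. The downside is a slightly smaller difference in primary care use between arms.

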7.7.2.1 Intervention group participants with an existing primary care provider

For intervention group participants who have a PCP, study staff will assemble a baseline provider communication packet that will include:

- Provider Letter (*HCU Letter 1 - T0 Current Pt INT*)
- Copy of the participant's signed HIPAA authorization form

This baseline letter provides background information on FAITH-DM, informs the provider that the participant has enrolled in FAITH-DM, identifies the participant's group assignment, discloses screening results (only for participants assigned to the intervention group), describes the HCUA process, and informs the provider that a care utilization survey will be sent at the participant's 6- and 12-month mark in the study. No action is requested of the provider at baseline.

The provider communication packet should be generated and sent (by fax or mail) within two weeks of the participant's enrollment in the study. A description of how the site can maintain a HIPAA compliant fax is contained in **section 3.2.1**.

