- If necessary, clients can also be provided with information about local emergency medical care (local Emergency Rooms and hospitals) if the client prefers or needs immediate medical attention.
- If necessary and/or at the client’s request, study staff can also call “911” to initiate the local emergency response system (EMS) to have the client evaluated by health care professionals onsite. Severe hyperglycemia accompanied by any of the following symptoms potentially constitutes a medical emergency and warrants activation of the EMS: nausea and/or vomiting, chest pain, abdominal pain, or altered mental status.
- Only hyperglycemia events where clients report symptoms and study staff respond/act (e.g. activating local EMS) are required to be reported as an adverse event.
 - Complete an Adverse Event Report and contact [name] within 24 hours of event.
 - These events should be reported in the MS Access database for all study participants.

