 - ii. For clients referred from the FOOD BANK with blood glucose results between 240 mg/dL – 399 mg/dL, or HbA1c results 9.0% - 12.9%, The Organization agrees to attempt contacting the clients within 1 week of referral to schedule a new appointment that will take place within 1 month from the date of referral.
 - iii. For clients referred from the FOOD BANK with a blood glucose result > 400 mg/dL, or with an HbA1c result > 13%, The Organization agrees to attempt contacting the client within 24-48 hours of referral to schedule a new appointment that will take place within 1 week from the date of referral.
 - b. The Organization will identify a staff person(s) that can be contacted by FOOD BANK staff so that study staff can verify The Organization attempted to contact and schedule appointments with clients referred for care from the FOOD BANK.
2. If the Organization does NOT accept direct referrals from any agency, then the FOOD BANK will provide clients needing care with written information, verbal instructions, and encouragement for the client to make a new appointment with their existing PCP or a new patient appointment at the Organization by using the Organization's existing patient appointment scheduling process.
3. The Organization can implement a process to identify any existing clinic patients who may be food-insecure or at risk for food-insecurity, and who may benefit from resources organized and/or managed by the FOOD BANK.
 - a. See attached document: *FAITH-DM FI Clinical Training Brief* for detailed information on how to screen patients for food insecurity and refer patients into the local hunger safety net.
4. The Organization will refer clinic patients to the FOOD BANK via existing food bank protocols for referrals.
5. NOTE: The Organization can NOT refer clinic patients directly into the FAITH-DM trial.
 - a. For Organization patients with diagnosed type 2 diabetes referred from the clinic to the FOOD BANK, FAITH-DM staff will use existing study protocols to recruit and enroll clients into the FAITH-DM trial.
6. When requested (but no more than quarterly), The Organization will provide FOOD BANK with data on referral processes and on FOOD BANK-referred clients that establish care with The Organization.

Health Care Utilization Analysis

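### Section 10.2 orders referral at glucose 240–399 mg/dL or HbA1c 9%–12.9%, but its sub-bullet, read literally, waives that referral for people without symptoms

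*Combined protocol and SAP*

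**What the plan says.** Section 10.2 divides high results into two bands.

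- **Middle band (glucose 240–399 mg/dL or HbA1c 9%–12.9%).** For an enrolled participant or a client not yet enrolled, "study staff should refer the client back to their primary care provider for evaluation". Someone without a primary care provider (PCP) is to get a new-patient referral to a partner clinic. No symptom condition is attached. The sub-bullet directly beneath reads: "Hyperglycemia in the absence of symptoms does not require action by study staff or reporting as an adverse event".
- **Severe band (glucose above 400 mg/dL or HbA1c above 13%).** Staff again refer. The matching sub-bullet reads: "Hyperglycemia in the absence of symptoms of study staff action does not require reporting as an adverse event". It waives reporting only.

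The section closes with a reporting rule limited to "Only hyperglycemia events where clients report symptoms and study staff respond/act", with activation of the local emergency service as its example.

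The draft food bank–clinic memorandum of understanding (MOU, Appendix O) provides for referrals in the same middle band: "The Organization agrees to attempt contacting the clients within 1 week of referral to schedule a new appointment". Item 3a of the food bank's duties commits it to refer at HbA1c of 9.0% or more when clients lack a provider or "if they state that they already receive care at The Organization". Neither clause depends on symptoms.

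**The concern.** The referral instruction and the sub-bullet cannot both be followed as written. An asymptomatic client with an HbA1c of 10% is to be referred and, one line later, needs nothing done by staff. The sub-bullet is the more specific of the two, so a reader would naturally take it as qualifying the bullet above.

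The manual is meant to be followed step by step, and testing is done by food bank staff and trained volunteers at three sites (Sections 1.2, 3.1.1 and 14.3). At stake are whether an asymptomatic person whose result the plan says needs evaluation is actually referred, and whether sites act alike. It is a question of safety and uniform conduct, not of inference.

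**Working it through.** No arithmetic applies. The check sets the relevant texts side by side.

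**Step 1: is there a conflict?** The trigger in the middle band is the test value alone. The sub-bullet joins two things with *or*, action by staff and adverse event reporting, and waives both when there are no symptoms. It therefore cannot be read as waiving reporting only. Making a referral is an action by staff, and nothing in 10.2 exempts it. The conflict is confined to asymptomatic people in the middle band; symptomatic people and the severe band are not affected.

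**Step 2: what was meant?** Five places point the same way.

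- The severe-band sub-bullet waives reporting only.
- The closing rule of 10.2 illustrates a staff response by calling the emergency service.
- The adverse event form (Appendix AN) links action to symptomatic clients.
- Section 10.1 uses a parallel construction for low glucose in people without a diabetes history; the paired verb there is treating on the spot.
- Section 10.2 and Appendix O set clinic contact within 1 week and an appointment within 1 month for this band. That is a routine pathway and makes little sense if only symptomatic people enter it.

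The intended meaning is no emergency response and no adverse event report, with the referral left standing.

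**Step 3: who is reached by another rule that does not depend on symptoms?** Everyone screened gets written results (3.1.1, Appendix J) and is directed to a provider or health center (5.1). Beyond that:

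| Person in the middle band | Other rule | What still rests on 10.2 |
|---|---|---|
| Intervention, no PCP at T0 | Active referral (3.2.1, 7.7.2.2) | Little |
| Intervention, PCP at T0 | Letter to the PCP with screening results (7.7.2.1) | Little |
| Control, no PCP at T0 | Resource handout (3.2.1, 7.7.2.4); draft MOU items 3 and 3a | Little, where the MOU applies |
| Control, PCP at T0 | The T0 letter "discloses screening results (only for participants assigned to the intervention group"; draft MOU item 3a if the PCP is at a partner clinic | PCP outside a partner clinic; glucose-only results |
| Not enrolled, no PCP | Faxed referral form (3.2.1) | Little |
| Not enrolled, PCP | "If food pantry client is not (and will not be) enrolled in FAITH-DM, provide resource hand out"; draft MOU item 3a if the PCP is at a partner clinic | PCP outside a partner clinic; glucose-only results |
| Raised follow-up result | Encouragement to contact the PCP in 1-on-1 contacts (3.4.2); active referral at T6 and T12 only if no PCP (3.2.1); draft MOU item 3a | PCP outside a partner clinic; glucose-only results |

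Where a partner clinic takes no direct referrals, draft MOU item 4 substitutes written information, verbal instructions and encouragement to book. Item 3a is triggered by HbA1c only, which is why results raised on glucose alone remain in the last column. The T3 and T9 tests in 3.1.4 have no check of PCP status attached.

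**The case against.** The strongest reply is that context settles the wording. The sentence sits under an express order to refer, in a section on adverse event reporting, and the texts in step 2 show what was meant. Moreover, for someone who has a PCP, 10.2 only tells staff to refer the client back; it specifies no form, fax or call. Section 5.1 already has staff direct every screened client to a provider, so the practical difference may be small. Under Section 9.1, most follow-up tests coincide with a food-box pickup and 1-on-1 education, where 3.4.2 calls for encouragement to contact the PCP; the intervention arm's T12 test is the exception. Training (5.1), weekly calls (2.8) and site monitoring (14.2) could catch divergent practice.

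Much of this stands. It rules out two stronger inferences that a reader might draw:

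- **That the plan means to withhold referral from asymptomatic people.** The severe band, the clinic timelines and the draft MOU all contradict this.
- **That controls with a PCP, non-enrolled clients with a PCP and people with raised follow-up results depend wholly on 10.2.** Draft MOU items 3a and 4, together with 5.1 and 3.4.2, give many of them a referral or advice.

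It does not remove the conflicting sentence. Staff should not have to combine 10.1, an adverse event form and a draft clinic agreement to learn whether to refer. Advice to see a doctor is also not the referral that 10.2 orders, and the MOU is a template that does not reach PCPs outside partner clinics.

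**Conclusion.** The contradiction is real and the intent behind it is clear. It is a low-severity defect in the wording of an operative safety rule. The remaining exposure is mainly asymptomatic people with a PCP outside a partner clinic (controls at T0, clients not enrolled, and raised follow-up results), plus results raised on glucose only. This assumes that the draft MOU is adopted broadly as written; where it is not, more people rest on 10.2.

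The size of that exposure cannot be estimated. The documents give neither the asymptomatic share, nor the share with a PCP outside partner clinics, nor the number of non-enrolled clients in the band. A reader might model the HbA1c distribution from the assumptions in Section 13.4.1 and take everyone in the band as affected. That would count intervention participants and others already reached by other rules, and would leave out non-enrolled clients, so it does not measure the defect.

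The primary analysis, sample size and error rates are unaffected.

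**What to change.** In the middle-band sub-bullet of 10.2, replace the waiver with: *does not require emergency action or reporting as an adverse event; the referral above still applies*. In the severe-band sub-bullet, change the first *of* to *or*, so that it refers to symptoms or staff action.

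The cost is a few words in one section and a short notice to the three sites. No procedure, form, data item or analysis changes, and staff who already read the rule as intended will see no difference.
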